9.0 Statistical Considerations

Power:

Hypothesizing a 6 minute decrease in total operative time for the Moses laser group, a sample size of 146 patients per group across all sites will have 80% power to detect a 20% decrease in the total procedure time. If a 5% dropout rate is assumed, the total sample size will be 300 patients. Mean operative time

Vanderbilt University Medical Center
Department of Urologic Surgery
[name]
[name]
for dusting using non-Moses settings was estimated as 35.9 minutes +/- 17.8 min based on results from a previous dusting trial (12).

Data Management:

The electronic data will be stored in the REDCap (Research Electronic Data Capture) application (13,14). REDCap is a stand-alone system with no interaction or connectivity to other systems, and the database is located behind the VUMC firewall. Users must have a VUMC provided ID/password to connect to REDCap and their ID must be specifically authorized in order to access an individual study's data. All changes to the data, and each "record viewed" is logged back to the individual ID with a timestamp. When the case report forms are configured, each field has an attribute that can be set to flag it as an "identifier". This "identifier" is used by REDCap to control certain actions related to the field. REDCap also has several built-in functions to control the exporting of identifying information. Individual users are each granted specific export rights, including – None, De-Identified, and Full. Additional export de-identification options include removing identifiers and dates, hashing IDs and date shifting. Centers will be put into Data Access Groups so that they only have access to their own data and not that of other sites. The data center (VUMC) will be the only center will access to the full dataset.

Statistical Analysis:

Intention-to-treat analysis will include all randomized subjects. Demographic data and pre-operative and post-operative data for each treatment group will be summarized using median and quartiles (continuous variables) and frequency and percent (categorical variable). Baseline data will not be compared across treatments as this is a randomized study.

The primary outcome is total operative time, and it is assumed to have a strong correlation with the stone size. A linear regression model will be fit with total operative time as the response variable and the treatment (Moses vs non-Moses) and stone size as the main covariates. An interaction term between the treatment and total operative time will be included in the model to allow for treatment effect estimation at a specific value of stone size. Using this model, we will be able to estimate the difference in total operative time with a 95% confidence interval at a given stone size and if the treatment effect is uniform across stone size. Statistically significant treatment effect on the primary outcome is required to conclude treatment effect.

The secondary outcomes (stone retropulsion and visibility) will be analyzed with the same regression model. Factorial ANOVA will be used to determine any

Vanderbilt University Medical Center
Department of Urologic Surgery
[name]
[name]

interaction between Moses utilization and stone size on workload as measured by NASA-TLX. Surgeon prediction of Moses utilization will be compared to the actual setting using chi-squared tests. Stone free rates and complications will be compared using Fisher's exact test. Odds ratios and a 95% confidence interval will be used to quantify treatment-effect difference on these endpoints.

An interim analysis will be performed using a group sequential design to assess if the study can be stopped early. This will be performed at enrollment milestones of n=150 and n=230.

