Demographic fields that will be obtained preoperatively include age, race, gender, ASA (American Society of Anesthesiologists) score (for comorbidity assessment), height, weight, body mass index (BMI), and prior stone disease. Disease fields that will be obtained include stone size (maximal axial and coronal dimensions), degree of hydronephrosis (mild/moderate/severe), and prior ureteral stenting or nephrostomy tube placement.

Perioperative fields will include total operative time, procedure time, laser time, laser fiber size, settings of lithotripsy (rate, energy), total laser energy used, anesthesia time, type of anesthesia, use of active fragment extraction (beyond that for analysis/culture), 1st assist skill level, use of ureteral access sheath, intra-operative complications, and treatment on any anticoagulation.

Postoperative fields will include length of hospitalization, postoperative complications, stone composition, need for ancillary procedures, stent duration, and stone-free status on postoperative CT imaging.

The degree of intra-procedure stone retropulsion and visibility will be assessed using a Likert scale by blinded video review consisting of 3 individuals. Adequacy of dusting will be graded as a binary variable. Video clips comprising the first 20 seconds and the last 20 seconds of dusting should be recorded. Blinded reviewers will be surgeons who specialize in ureteroscopy and are not employed by a study center.

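### The power statement's 20% decrease does not match its 6-minute target, which is 16.7% of the stated control mean; 146 per group fits 6 minutes, and the outcome label and dropout arithmetic need tidying

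*Combined protocol and SAP*

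**What the plan says.** All the design figures are in section 9.0 (Statistical Considerations) of the combined protocol and SAP, under Power.

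- The sentence opens with an absolute target: "Hypothesizing a 6 minute decrease in total operative time for the Moses laser group".
- It ends with a relative target on a differently named outcome: "146 patients per group across all sites will have 80% power to detect a 20% decrease in the total procedure time".
- Mean operative time for non-Moses dusting "was estimated as 35.9 minutes +/- 17.8 min". No other mean or SD is given for sizing the trial.
- On the total: "If a 5% dropout rate is assumed, the total sample size will be 300 patients".

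The paragraph states no alpha, sidedness or test. Under Statistical Analysis, the same section says: "The primary outcome is total operative time, and it is assumed to have a strong correlation with the stone size". Section 5.0 (Study Procedures) lists operative time and procedure time as separate data fields: "Perioperative fields will include total operative time, procedure time, laser time".

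**The concern.** A percentage decrease in the Moses group is naturally read against the non-Moses mean. On that reading, 6 minutes and 20% cannot describe the same effect, yet one sentence gives both as the target. The target effect is the benchmark against which the result will be judged. A reader who takes the percentage at face value will believe that the trial was sized at 80% power for 7.18 minutes, which is 1.18 minutes more than the stated 6.

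Two smaller matters sit in the same lines. The power is attached to procedure time, which is a field of its own with no mean or SD given. And 146 per group, 5% dropout and a total of 300 do not obviously follow from one another.

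**Working it through.** **Inputs from section 9.0:** effect 6 min; control mean 35.9 min; spread 17.8 min; 146 per group; power 80%; dropout 5%; total 300. Allocation is 1:1 (section 4.0).

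**Assumed:** 17.8 is an SD and applies to both arms; alpha is two-sided 0.05, in line with the planned 95% confidence interval; single look; no covariate adjustment.

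**Step 1. Percentages (no assumption needed).**
- 6 / 35.9 = 16.7%
- 0.20 × 35.9 = 7.18 min
- Implied Moses mean: 35.9 − 6 = 29.9 min, and 6 / 29.9 = 20.1%
- 6 min is exactly 20% only of 6 / 0.20 = 30.0 min, a baseline that the document does not give.

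**Step 2. Reproducing 146.** The normal approximation is n per group = 2 × [SD × (1.960 + 0.842) / difference]².
- 6 min: 2 × (17.8 × 2.802 / 6)² = 138.2, so 139; by t-test 139.1, so 140.
- 7.18 min: 2 × (17.8 × 2.802 / 7.18)² = 96.5, so 97; by t-test 97.4, so 98.

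The plain calculation for 6 min falls a little short of 146, but ordinary variants reach it. The rank-test efficiency adjustment gives 139.1 × π/3 = 145.7, so 146. Inflating for 5% dropout gives 139 × 1.05 = 146, or 139.1 / 0.95 = 146.4, so 147. The document does not say which route, if any, was used. For 7.18 min the rank-test adjustment and the division by 0.95 give only 102.0 and 102.6.

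**Step 3. Power at 146 per group.** SE = 17.8 × √(2/146) = 2.083 min.

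| True difference | Difference / SE | Power, normal approximation | Power, t-test |
|---|---|---|---|
| 6 min | 2.880 | 82.1% | 81.9% |
| 7.18 min | 3.446 | 93.1% | 93.0% |

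The difference detectable with 80% power at 146 per group is 2.802 × 2.083 = 5.84 min, or 16.3% of 35.9.

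**Step 4. How far the assumptions matter.**

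| Assumption | n per group, 6 min | n per group, 7.18 min |
|---|---|---|
| SD 16.4, two-sided 0.05 | 118.2 | 82.9 |
| SD 17.8, two-sided 0.05 | 139.1 | 97.4 |
| SD 20, two-sided 0.05 | 175.4 | 122.8 |
| SD 17.8, one-sided 0.05 (normal approximation) | 109 | 76 |

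For 146 to match 7.18 min, the SD would have to be about 21.8 rather than 17.8, or two-sided alpha about 0.01 (0.0097).

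**Step 5. Dropout.** If 146 is the evaluable number, 292 / 0.95 = 307.4, so 308 are needed. A total of 300 then covers a loss of 8 / 300 = 2.7%. Conversely, 300 × 0.95 = 285 evaluable, about 142 per group, with 80.8% power for 6 min by t-test.

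**The case against.** The best defence is that nothing of substance is wrong. The absolute target comes first in the sentence and is unambiguous, 146 per group is recovered for 6 minutes by a standard adjustment, and 300 randomised still leaves about 81% power after 5% loss. Number of patients, analysis and conduct are unaffected. All of that stands, and it limits the point to a correction of text. It does not rescue the percentage, which is wrong on the only baseline given.

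Four stronger readings are tempting, and the documents do not support them.

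- *The trial is powered for the wrong endpoint.* The sentence opens with total operative time, and the mean and SD are operative-time figures. The later term looks like a mislabel. It still needs correcting, because procedure time is also collected.
- *The trial is too small, or eight patients short.* The figure of 308 holds only if 146 is before dropout. Step 2 shows routes by which 146 could already include it.
- *The 20% is known to be 6 / 29.9.* The arithmetic fits closely, but the document does not show the calculation.
- *The true power is some other definite figure once the interim looks and stone size are counted.* The plan sets looks ("This will be performed at enrollment milestones of n=150 and n=230") but gives no boundary and does not say whether early stopping is for efficacy or futility, so any loss of power cannot be fixed. Nor can one say without condition that adjusting for stone size raises power. The planned model has an interaction and estimates the effect at a given stone size. If sizes were uniform on 8–20 mm and stone size explained 10–40% of the variance (all assumed), power for 6 minutes on 285 patients would be about 85–96% at 14 mm but only about 32–45% at 8 mm.

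**Conclusion.** Wrong as written, and a wording correction. The mismatch between 6 minutes (16.7% of 35.9) and 20% (7.18 minutes) needs no assumption. That 146 per group belongs to the 6-minute target rests on a common SD of 17.8 and two-sided alpha 0.05: about 82% power for 6 minutes against about 93% for a true 20% reduction from control. The overstated figure is therefore the percentage, and the trial is not undersized because of it. The outcome label is a probable slip. The dropout arithmetic is unexplained, at little cost in power.

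**What to change.** Keep the total at 300 and state one target. Suggested text, for the sponsor to confirm the SD, alpha and test:

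> 300 randomised, about 285 evaluable after 5% loss (about 142 per group). With a non-Moses mean total operative time of 35.9 min, SD 17.8 min and two-sided alpha 0.05, an unadjusted, single-look comparison has about 81% power to detect a 6-minute reduction (16.7% of 35.9 min).

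Delete the 20% or give its denominator. Use total operative time throughout the power paragraph. Say whether 146 is before or after dropout, and show how 146, 5% and 300 fit together. Add no sentence on the effect of the interim looks or of stone-size adjustment on power: the boundary and the estimand that it would need are not stated.

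If the sponsor did mean 20% of the control mean, the 6-minute figure has to change instead, and the stated 80% would then understate the power.

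The cost is protocol wording, with no added patients, visits or data. The downside is a less favourable stated percentage, 16.7% instead of 20%.

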3.0 Inclusion/Exclusion Criteria

Inclusion criteria:

- Solitary renal stone 8 to 20 mm in size or in the case of multiple stones the conglomerate diameter (additive maximal diameter of all stones on axial imaging of computed tomography) of 8-20 mm is required
- Must be a suitable operative candidate for flexible ureteroscopy per urologic guidelines (1)
- Must be 18 years or older
- Must be able to give consent

Exclusion criteria:

- Concomitant stones in the ureter

Vanderbilt University Medical Center
Department of Urologic Surgery
[name]
[name]

- Prior ipsilateral upper urinary tract reconstructive procedures or history of ipsilateral ureteral stricture
- Prior radiotherapy to the abdomen or pelvis
- Neurogenic bladder or spinal cord injury
- Pregnancy
- Untreated UTI

Attending surgeons participating in the study must be urological surgeons specializing in kidney stones.

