4.0 Enrollment/Randomization

The trial will be a prospective, randomized, double blind study of patients with renal stones 8-20 mm in size located at or above the level of the ureteropelvic junction. This is a multi-institutional study and will collaborate with the Cleveland Clinic, Columbia University, Duke University, University of California San Diego, Indiana University, and Mayo Clinic (Arizona) using an identical protocol. Total enrollment will be limited to 300 patients for the study with each site having a goal of up to 100 patients, understanding that some sites may recruit less than their goal. Each site is responsible for its own IRB approval. Ureteroscopic treatment of renal calculi is a standard of care treatment approach, and in the course of participating in this study no treatments will be performed that are not considered standard of care.

Patients will be identified based on clinic visits or hospital admission.

Patients will be randomized on a 1:1 basis to standard holmium laser lithotripsy dusting settings or holmium laser lithotripsy using Moses technology. All surgeons will be blinded to the randomization and only the laser technician will know the randomization. The randomization will be stratified by centers and also by renal stone size (8.0-12.0mm, 12.1-16.0mm, 16.1-20.0mm). Block sizes of 2, 4, and 6 will be used within each stratum to enhance blinding. The randomization system will be developed using R, implemented using RedCap and maintained in the Center for Quantitative Sciences server at Vanderbilt.

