5.0 Study Procedures

Procedures performed in this study that are standard of care:

Patients will be identified based on clinic visits or hospital admission. All patients will be counseled on standard treatment options – extracorporeal shock wave lithotripsy (ESWL), percutaneous nephrolithotomy (PCNL) and ureteroscopy (URS). The discussion regarding treatment options and subsequent care will not

Vanderbilt University Medical Center
Department of Urologic Surgery
[name]
[name]

deviate from routine care. Those selecting URS will be enrolled to have data collected prospectively. Patients will be consented prior to surgery for collection of demographic, disease, perioperative, and postoperative data. Abdominopelvic computed tomography (CT) will be used to delineate pre-operative stone size, with measurements captured in greatest axial and coronal dimensions. A preoperative abdominopelvic CT will be obtained if one is not available as clinically indicated per urologic guidelines (1).

Patients will have flexible URS performed in standard fashion, without deviation from the standard of care. The patient will be brought to the operating room and given general or regional anesthesia per anesthesia and patient preference. The patient will be placed in lithotomy position and prepared and draped in standard fashion. Rigid cystoscopy will be performed and a flexible guidewire will be placed through the ipsilateral ureter to the kidney under fluoroscopic guidance. A second wire will be placed at the discretion of the surgeon. Ureteral dilation will be performed at the discretion of the surgeon. A ureteral access sheath will be used at the discretion of the surgeon. Flexible URS and holmium laser lithotripsy will be performed using a dusting technique for stone fragmentation. For all patients, a Moses laser fiber will be utilized.

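### Allocation is stratified by center but the primary operative-time model names no center term; if centers differ, the interval is wider than it need be and the test is conservative

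*Combined protocol and SAP*

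**What the plan says.** Section 4.0 (Enrollment/Randomization): "The randomization will be stratified by centers and also by renal stone size", in three size bands, with permuted blocks of 2, 4 and 6 in every stratum. Six institutions are named as collaborators with the coordinating center, which makes seven sites. The section expects uneven recruitment, "understanding that some sites may recruit less than their goal".

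Section 9.0 (Statistical Analysis) specifies a linear regression with "total operative time as the response variable and the treatment (Moses vs non-Moses) and stone size as the main covariates". It adds an interaction, intended "to allow for treatment effect estimation at a specific value of stone size". A significant treatment effect on this outcome is required before any effect is concluded. Of the interim analysis it says: "This will be performed at enrollment milestones of n=150 and n=230".

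Center appears in the allocation scheme and in the REDCap access arrangements, but in no analysis. Of the two stratification factors, stone size enters the model and center does not.

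**The concern.** Blocking within center balances the arms inside each site, so differences between sites largely cancel from the treatment comparison. The precision is gained at randomization, but the analysis recovers it only if the model knows about center. Otherwise the between-center variation stays in the residual variance and the reported standard error exceeds the true one. The 95% interval then covers more than 95%, the test rejects less than 5% of the time under the null, and part of the benefit of the stratified design goes unused.

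The document points both ways on how far centers differ. In favor of small differences are "Mayo Clinic (Arizona) using an identical protocol" and, in section 3.0, "Attending surgeons participating in the study must be urological surgeons specializing in kidney stones". Against that, section 5.0 leaves several time-consuming steps to the operator, for example "A ureteral access sheath will be used at the discretion of the surgeon". Ureteral dilation and a second wire are treated the same way. Such choices may vary as much within centers as between them.

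**Working it through.** **Inputs from section 9.0.** 146 patients per group (292 in all), a 6-minute effect, SD 17.8 minutes. Two-sided 5% is inferred from the 95% interval, since no alpha is stated.

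**The plan's own figure.** n per group = 2 × (1.96 + 0.8416)² × (17.8/6)² = 138.2, so 139. At 146 per group the standard error is 17.8 × √(2/146) = 2.083 and power is Φ(6/2.083 − 1.96) = 82.1%. This is consistent with the stated 80%.

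**Assumptions.** The between-center share of total variance is not given; 0, 2, 5, 10 and 20% are used. The 17.8 is treated as a total SD that already includes center, because the title of the cited dusting trial describes it as multicenter. The size-time correlation is set at 0.4 and varied. Stone size is uniform on 8–20 mm. The interaction is taken as treatment by stone size, which its stated purpose requires, although section 9.0 writes it with operative time. The effect is constant and tested at 14 mm, in a single look with no sequential boundary, since none is stated.

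**Closed form, correlation 0.4 (r² = 0.16), perfect balance within center.**
- Reported SE without center = 17.8 × √(1 − 0.16) × √(2/146) = 1.909, whatever the share.
- True SE = 17.8 × √(1 − 0.16 − share) × √(2/146) = 1.909, 1.887, 1.852, 1.792, 1.667 at the five shares.
- Power without center = Φ((6 − 1.96 × 1.909)/true SE); with center = Φ(6/true SE − 1.96).
- At a 10% share: Φ(2.258/1.792) = 89.6% against Φ(6/1.792 − 1.96) = 91.7%. Type I error without center = 2 × [1 − Φ(1.96 × 1.909/1.792)] = 3.7%.

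**Simulation.** Seven equal sites × three size bands, blocks of 2/4/6 within stratum, least squares with and without center indicators, 10,000 trials per row:

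| Center share | Mean SE without / with | 95% half-width with center (min) | Power without / with (%) | Type I error without (%) |
|---|---|---|---|---|
| 0% | 1.911 / 1.912 | 3.76 | 88.0 / 87.9 | 5.3 |
| 2% | 1.913 / 1.891 | 3.72 | 87.7 / 88.3 | 4.7 |
| 5% | 1.912 / 1.856 | 3.65 | 88.7 / 90.0 | 4.2 |
| 10% | 1.913 / 1.796 | 3.54 | 89.3 / 91.5 | 3.7 |
| 20% | 1.914 / 1.670 | 3.29 | 90.7 / 94.8 | 2.8 |

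The half-width without center is 3.76–3.77 throughout. Type I error with center is 4.7–5.3% (Monte Carlo SE about 0.2). Incomplete blocks explain why the simulated effect is slightly smaller than the closed form (2.8% against 2.5% type I error at a 20% share).

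**Sensitivity.**
- Power gain at 5, 10 and 20% shares: 1.5, 2.6 and 4.8 points at correlation 0.2; 0.8, 1.5 and 1.6 points at correlation 0.6.
- Unequal sites (assumed 100/60/50/40/25/15/10 of 300), correlation 0.4: power 88.7/89.8, 89.3/91.5 and 90.5/94.5% at the same shares.
- Stone size explaining nothing, unequal sites, 5,000 trials, 10% share: full interval width 8.20 to 7.79 minutes, power 82.8 to 85.6%.
- Cause: in that last setting at a 20% share, type I error without center is 3.2% under stratified allocation and 4.8% under unstratified allocation. The conservatism therefore comes from leaving out a stratification factor.
- Interim looks, unequal sites, half-width without/with center at a 10% share: 5.27/4.97 minutes at n=150 and 4.25/4.00 at n=230.

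**The case against.** The harm is conditional and may be small. No between-center variance is given, and at a 2% share the gain is too small to matter. At correlation 0.4, the half-width shrinks by 3.77 − 3.65 = 0.12 minutes (7 seconds) at a 5% share and 3.77 − 3.54 = 0.23 minutes (14 seconds) at 10%, against a 6-minute effect. Section 9.0 expects stone size to correlate strongly with time; at correlation 0.6 power without center is already above 95% at these shares and the gain is under 2 points. All of this stands, and it makes the point one of efficiency and not validity.

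The figures also depend on choices the plan does not make. At 8 or 20 mm the standard error is about double that at 14 mm, and power without center differences is about 35%, not 88%. So the absolute power figures belong to the 14 mm estimand. The relative gain carries over: at 8 mm and a 10% share the SE falls from 3.83 to 3.60, about 6%, as at 14 mm. The type I errors are single-look values and not the trial's overall error rate.

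The wording of the model does not exclude further terms. But a term that is merely permitted is not prespecified, and two interim looks make it important to settle the model beforehand.

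Finally, each site answers to its own IRB, so amending a shared document carries some administrative cost. That is a real but small cost.

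**Conclusion.** The point holds. Center is used in allocation and in no analysis, and the direction of the effect is certain: if centers differ, the interval over-covers and the test is conservative. There is no bias, no inflation of false positives and no loss against the stated 80% power.

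The size is not known. Under an assumed correlation of 0.4, the power gain is about 1 point at a 5% center share, 2 at 10% and 4 at 20%, with type I error without center of 4.2, 3.7 and 2.8%. These figures assume a total SD of 17.8, a treatment-by-stone-size interaction, a test at 14 mm and one look.

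The recommendation does not depend on the unknown share, because adding center costs almost nothing when centers are alike. The change should be made, but it does not repair a validity failure.

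**What to change.** Add to the primary analysis in section 9.0:

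> The primary model will contain treatment, continuous stone size, their interaction (so that the treatment effect can be estimated at a chosen stone size) and center as a fixed effect, with one indicator for each enrolling site after the first. The same model will be fitted at the looks at n=150 and n=230 and at the final analysis.

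Do not let the data decide whether center stays in. If very small sites are a worry, choose a random intercept for center instead, once and before the first look, and keep it throughout. The retropulsion and visibility analyses may carry the same term for consistency; no gain has been shown there.

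Cost: two sentences, with whatever amendment the sites' IRBs require. Center is already recorded for allocation and for the REDCap access groups. Seven sites use six degrees of freedom: residual degrees of freedom go from 292 − 4 = 288 to 282. With no center differences the simulated standard error goes from 1.911 to 1.912 (equal sites) or 1.910 to 1.913 (unequal sites) at 292 patients. At n=150 with unequal sites, the smallest expected to hold 5 patients, it goes from 2.667 to 2.680. A fixed effect is therefore workable at every look.

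### The primary model interacts treatment with its own response, total operative time, where stone size is meant, and no contrast is named to decide the trial

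*Combined protocol and SAP*

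**What the plan says.** Section 9.0 (Statistical Analysis) fits a linear regression with total operative time as the response and treatment and stone size as main covariates. Of operative time it says "it is assumed to have a strong correlation with the stone size". It then adds: "An interaction term between the treatment and total operative time will be included in the model to allow for treatment effect estimation". The same sentence gives the purpose as "to allow for treatment effect estimation at a specific value of stone size", and the next promises the difference with a 95% confidence interval "at a given stone size and if the treatment effect is uniform across stone size".

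The success rule is: "Statistically significant treatment effect on the primary outcome is required to conclude treatment effect". No coefficient, stone size, average or joint test is named, and no significance level is given. The model is reused: "The secondary outcomes (stone retropulsion and visibility) will be analyzed with the same regression model".

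The Power paragraph of the same section rests on one overall difference, "Hypothesizing a 6 minute decrease in total operative time for the Moses laser group", and on a control mean "for dusting using non-Moses settings was estimated as 35.9 minutes +/- 17.8 min". The hypothesis in section 1.0 likewise concerns stone burdens of 8–20 mm taken together.

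**The concern.** There are two faults, one behind the other.

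**The term.** With total operative time as the response, a treatment × total operative time term puts the response on both sides of the equation. It also leaves out treatment × stone size, the only term that can deliver the size-specific effects the plan promises. For retropulsion and visibility the inherited term fails differently. Operative time is not the response there, but it is measured after randomisation and is what treatment is expected to change. Such a model would run without any obvious warning.

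**The decision.** Once the term is corrected, there is a different treatment effect at every stone size, so a requirement for a significant treatment effect no longer identifies one test. The trial's conclusion hangs on that requirement. Two interim looks are planned, at 150 and 230 enrolled, so the choice could be made after data have been seen.

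**Working it through.** **Inputs from section 9.0.** 146 per group; difference 6 min; control mean 35.9 min; SD 17.8 min; 5% dropout. Eligible stone size is 8–20 mm (section 3.0).

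**Assumptions, because the plan gives no figure.** Two-sided 5% level, inferred from the 95% interval. Stone size uniform on 8–20 mm, so mean 14 mm and SD 12/√12 = 3.46 mm. Size–time correlation ρ of 0.5 to 0.7 as a reading of a strong correlation, with 0 as the lower bound. No adjustment for interim looks.

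**1. The plan's own figure.** For a plain comparison of two means, n = 2(1.96 + 0.84)² × 17.8²/6² = 138.2, or 139 per group. Allowing for 5% dropout, 138.2/0.95 = 145.4, or 146. Without the dropout step, 146 per group gives 81.9% power (t test). The planned size therefore fits one unadjusted average difference, and it does not come from an interaction model.

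**2. The model as written**, Y = a + bT + cS + d(T×Y), with Moses T = 1 and time uncentred. In the Moses arm T×Y is Y itself. Setting d = 1, b = −a and c = 0 reproduces every Moses observation exactly, whatever the treatment does. At ρ = 0, a is about 35.9, so b is about −35.9. Simulation with no treatment effect (6,000 trials per setting):

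| ρ | mean treatment coefficient (min) | rejected |
|---|---|---|
| 0 | −35.9 | 100% |
| 0.5 | −30.8 | 100% |
| 0.7 | −24.2 | 100% |

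**3. The corrected model**, Y = a + bT + cS + d(T×S). At stone size x₀ the standard error of the treatment difference is

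SE(x₀) = 17.8 × √(1 − ρ²) × √(2/146) × √(1 + ((x₀ − 14)/3.46)²).

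- At 14 mm the last factor is 1, so SE = 2.08, 1.80 and 1.49 min for ρ = 0, 0.5 and 0.7.
- At 8 or 20 mm it is √(1 + 36/12) = 2.
- At 0 mm it is √(1 + 196/12) = 4.16. This is what the treatment coefficient estimates if stone size is entered in mm without centring.

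Power for a uniform 6-minute benefit:

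| Test | ρ = 0 | ρ = 0.5 | ρ = 0.7 |
|---|---|---|---|
| Contrast at mean stone size | 82% | 91% | 98% |
| Main-effects model, no interaction | 81% | 91% | 98% |
| Joint 2-df test of treatment and interaction | 73% | 85% | 96% |
| Contrast at 8 or 20 mm | 30% | 38% | 52% |
| Uncentred treatment coefficient (0 mm) | 10% | 12% | 16% |

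**4. Type I error.** Each of these tests, fixed in advance, holds about 5%. Counting success when either the mean-size contrast or the interaction is significant gives 9–10% over the range of ρ.

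**The case against.** The strongest reply is that the slip corrects itself. The faulty sentence and the one after it both speak of stone size, and the NASA-TLX analysis in the same section correctly pairs Moses use with stone size. No competent analyst would fit the literal model, so the 100% figure measures an analysis nobody will run. On the reading that sections 1.0 and 9.0 favour, an average effect, type I error is about 5% and power is at or above plan. The damaging alternatives are hypothetical: nothing says that a contrast at the end of the range decides, or that a significant interaction counts as success.

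Much of this is right. The 100% figure shows only that the text is invalid. The either/or rule is an illustration. The end-of-range powers depend on the assumed size distribution: with mean 12 mm and SD 3 mm instead, and ρ of 0.5 to 0.7, the same formula gives 51–67% at 8 mm and 21–29% at 20 mm. The literal failure in step 2 also does not transfer as such to retropulsion and visibility, where the problem is conditioning on a post-randomisation variable. Whether linear regression suits Likert ratings is a separate question.

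Two things remain. The only statement of the primary model is wrong, and no other text corrects it. Correcting it still leaves the decision test unnamed, because the average-effect reading has to be inferred from other paragraphs. The easiest mistake, reading the uncentred treatment row from the output, has under 20% power.

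**Conclusion.** The concern holds and should be fixed before any analysis by arm. The primary model as written is invalid, and its evident correction does not fix the success criterion. Under the stated assumptions the choice of contrast moves power for the planned 6-minute difference from 91–98% at mean stone size (82% with no correlation) to 38–52% at either end of the range (30%), and to 10–16% for an uncentred coefficient.

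The exact figures depend on the assumed size distribution and correlation. The ordering does not: a contrast at mean stone size is more precise than one well away from it. If the analysis team makes the likely correction and tests at mean stone size, nothing is lost. The fault is that the plan does not commit them to it.

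**What to change.** In section 9.0:

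1. Replace the interaction term with treatment × stone size, with stone size centred at its sample mean, and state that this corrected form is the one carried to retropulsion and visibility.
2. Add one sentence naming the two-sided treatment contrast at mean stone size as the sole decision test, with its significance level. The treatment coefficient from the main-effects model is a nearly equivalent choice. Either matches the single 6-minute difference used for sample size.
3. State that the interaction test and the size-specific differences, with 95% confidence intervals, are secondary and cannot by themselves establish a treatment effect.

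The change should be dated before the first interim look. It costs one corrected phrase and a short addition, needs no extra data or patients, and loses no power.
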